## **1. BACKGROUND**

### **1.1 PATHOPHYSIOLOGY**

Neovascular AMD is typically characterized by choroidal neovascularization (CNV) in the macular region. The choroidal capillaries and associated collagenous matrix proliferate and penetrate Bruch's membrane to form a fibrovascular "membrane" external to the retinal pigment epithelium (RPE), which may then extend through the RPE into the subretinal space. In some cases, however, the presence of an apical/subretinal fibrovascular membrane is not accompanied by a fibrovascular lesion on the basolateral/choroidal side of the RPE. Moreover, in some cases of neovascular AMD, there is strong angiographic evidence that the new vessels are supplied from the retinal circulation rather than from the choroidal circulation. The increased permeability of the newly formed capillaries can lead to accumulation of serous fluid or blood under the RPE or between the RPE and the sensory retina. If the center of the macula becomes detached, central vision is impaired. Retinal hemorrhage or involution of the new vessels is accompanied by fibrous metaplasia and organization that can result in an elevated subretinal mass called a disciform scar (D'Amico 1994).

The stimuli that produce CNV are unknown. However, there is strong evidence suggesting that angiogenic factors, such as vascular endothelial growth factor (VEGF), play a role in the pathogenesis of AMD (Eyetechnology Study Group 2003; Rosenfeld 2006, Brown 2006).

### **1.2 TREATMENT OF AGE RELATED MACULAR DEGENERATION**

The T-REX trial will address patients with treatment naive wet age-related macular degeneration (AMD).

The introduction of pharmaceuticals that target VEGF-A revolutionized the management of wet AMD. VEGF-A is a diffusible cytokine that stimulates angiogenesis and vascular permeability. Clinical blockage by intravitreal injection of biological agents such as ranibizumab, bevacizumab and aflibercept is well tolerated and remarkably effective against choroidal neovascularization (CNV) in AMD patients.

### **1.3 RANIBIZUMAB AND AGE RELATED MACULAR DEGENERATION**

Such efficacy was initially demonstrated with ranibizumab in two landmark trials, MARINA and ANCHOR (Minimally Classic/Occult Trial of the Anti-VEGF Antibody Ranibizumab in the Treatment of Neovascular AMD and Anti-VEGF Antibody for the Treatment of Predominantly Classic CNV in AMD). For the first time, patients with CNV secondary to AMD experienced an average visual improvement with over 90% of eyes losing less than 15 letters and about 30% of eyes gaining significant vision. Ranibizumab was FDA approved on June 30, 2006.

## **1.4 NONCLINICAL EXPERIENCE WITH RANIBIZUMAB**

### **1.4.1 Nonclinical Pharmacokinetics**

The pharmacokinetics of ranibizumab have been investigated in rabbits and cynomolgus monkeys following intravitreal and intravenous administration. In both species, following intravitreal administration, ranibizumab was cleared from the vitreous humor with a half-life of 2–3 days. Following single intravitreal administration to cynomolgus monkeys, retinal concentrations of ranibizumab were approximately one-third of vitreous concentrations and declined in parallel with vitreous concentrations. In humans, the intravitreal half-life of ranibizumab is estimated to be 7-8 days. Repeated intravitreal injections of ranibizumab can lead to detectable antibodies in serum in rabbits and cynomolgus monkeys.

### **1.4.2 Nonclinical Toxicology**

A series of nonclinical studies of ranibizumab administered by intravitreal injection to cynomolgus monkeys have been performed (details regarding study design and results can be found in the Investigator Brochure).

### **1.4.3 Nonclinical Data Supporting the Anti-Edema Activity of Ranibizumab**

In Studies 01-401E-1757 and 01-401G-1757, the effect of ranibizumab on vascular leakage was explored using a modified Miles assay in the guinea pig. Ranibizumab demonstrated a concentration-dependent effect of blunting the vascular permeability induced by VEGF. These results are consistent with the decrease in retinal vascular permeability as observed on optical coherence tomography (OCT) and fluorescein angiography in AMD and diabetic macular edema studies and further support the rationale for the use of ranibizumab in CRVO and BRVO, in which vascular permeability plays a significant role in the pathology

## **1.5 Clinical Experience With Ranibizumab**

Ranibizumab has been or is being studied in more than 5000 subjects with neovascular AMD in a number of Phase I, I/II, II, III, and IIIb clinical trials. Ranibizumab is contraindicated in patients with ocular or periocular infections and in those with known hypersensitivity to ranibizumab or any of the excipients in ranibizumab. Intravitreal injections, including those with ranibizumab, have been associated with endophthalmitis and retinal detachment. Proper aseptic injection technique should always be used when administering ranibizumab. Increases in IOP have been noted within 60 minutes of intravitreal injection with ranibizumab. Therefore, IOP as well as perfusion of the optic nerve head should be monitored and managed appropriately. Serious adverse events related to the injection procedure have occurred in <0.1% of intravitreal injections include endophthalmitis, rhegmatogenous retinal detachment, and iatrogenic traumatic cataract. Other serious ocular adverse events observed among ranibizumab-treated subjects and occurring in <2% of subjects included intraocular inflammation

and increased IOP. The most common adverse reactions (reported  $\geq 6\%$  higher in ranibizumab-treated subjects than control subjects) were conjunctival hemorrhage, eye pain, vitreous floaters, increased IOP, and intraocular inflammation.

Although there was a low rate ( $<4\%$ ) of arterial thromboembolic events (ATEs) observed in the ranibizumab clinical trials there is a potential risk of ATEs following intravitreal use of inhibitors of VEGF. The rate of ATEs in three studies (FVF2598g, FVF2587g, and FVF3192g) in the first year was 1.9% of subjects in the combined group of subjects treated with 0.3 mg or 0.5 mg ranibizumab compared with 1.1% of subjects in the control arms of the studies. In the second year of Study FVF2598g and FVF2587g, the rate of ATEs was 2.6% of subjects in the combined group of those treated with 0.3 mg or 0.5 mg ranibizumab compared with 2.9% of subjects in the control arm. The most common non-ocular adverse reactions observed in  $\geq 15\%$  of ranibizumab-treated subjects that occurred more frequently than in control subjects included, nasopharyngitis, headache, and upper respiratory tract infection.

The Sailor study (FVF3689g) evaluated the safety of intravitreal ranibizumab in a large population of subjects with CNV secondary to AMD. Subjects in Cohort 1 (N=2378) were randomized (1:1) to receive ranibizumab at a dose level of 0.3 mg or 0.5 mg; subjects were masked to these dose levels. Treatment was administered monthly for three initial doses (Day 0, Month 1, and Month 2), with scheduled follow-up visits on Months 3, 6, 9, and 12. Retreatment after the first three injections was performed as needed, on the basis of predefined criteria with injections no more frequently than every 30 days.

Cohort 2 (N=1992) consisted of subjects enrolled after the majority of Cohort 1 subjects had been enrolled, with enrollment continuing until ranibizumab was approved or denied by the FDA for US marketing, and if approved, until commercially available or 30 September 2006, whichever was earlier. Subjects in Cohort 2 received open-label ranibizumab at the 0.5 mg dose level, with an initial injection on Day 0 followed by retreatment at the physician's discretion, no more frequently than every 30 days. Subjects were monitored for safety for a total of 12 months; safety information, including both serious and nonserious adverse events, was collected at every clinic visit, with two formal safety visits scheduled at Months 6 and 12.

The study consisted of a 30-day screening period and a 1-year treatment period. Treatment duration was approximately 197 days for both dose groups in Cohort 1 and 144 days for subjects in Cohort 2. The mean follow-up time differed between Cohort 1 and Cohort 2, 337 days versus 254 days, respectively.

Ranibizumab was well tolerated, and the incidence of ocular SAEs and AEs was low and unrelated to dose. The rates of individual key ocular SAEs in Cohort 1 were  $< 1\%$  and were similar across dose groups. Endophthalmitis or presumed endophthalmitis developed in 0.2% subjects in the 0.3-mg group and 0.4%

subjects in the 0.5-mg group. The incidence of ocular inflammation, including iritis, uveitis, vitritis, and iridocyclitis was 1.9% in the 0.3-mg group and 1.5% in the 0.5-mg group. Overall cataract rates were 5.4% (0.3 mg) and 6.0% (0.5 mg) and were similar when broken down by nuclear, subcapsular, and cortical subtypes. The rates of individual key ocular SAEs in Cohort 2 were <1%.

The rates of key non-ocular SAEs and AEs, including Antiplatelet Trialists' Collaboration (APTC) ATEs, MI, and vascular death were similar for cohorts 1 and 2 and 0.3- and 0.5-mg dose groups. The incidence of MI and non-ocular hemorrhage was similar across Cohort 1 dose groups. APTC ATEs, including vascular and unknown deaths, nonfatal MI, and nonfatal cardiovascular accidents, were similar across dose groups. During the 12-month study period, 0.7% of subjects in the 0.3-mg group and 1.2% of subjects in the 0.5-mg group suffered a stroke. The number of vascular deaths and deaths due to unknown cause did not differ across dose groups. Rates of key non-ocular SAEs in Cohort 2 were generally lower than those in Cohort 1.

Refer to the Ranibizumab Investigator Brochure or Lucentis® Package Insert for additional details regarding clinical safety experience with ranibizumab.

## **2. Objectives**

This trial will assess the safety, tolerability and efficacy of a treat and extend management protocol for wet age related macular degeneration (AMD). Subjects will be randomized, 1:2, 1 (control arm-Cohort A) to 2 (comparator, treat and extend- Cohort B). Subjects in the control arm will receive monthly intravitreal injections of 0.5mg ranibizumab for 104 weeks and then be treated PRN for another 52 weeks. Subjects in the controlled arm will receive 3 monthly (visits 2, 4 and 5) intravitreal injections of 0.5mg ranibizumab followed by a treat and extend protocol. In a treat and extend protocol length between visits are increased by 2-week intervals, when there is no evidence of exudative disease activity present on ophthalmic exam or spectral-domain (SD)-OCT. In the treat and extend arm, the interval between injections will not exceed 12 weeks; specifically, subjects who are in the treat and extend Cohort B and do not exhibit exudative activity either by SD-OCT or clinical examination will receive mandatory study drug injection every twelve weeks. Subjects will receive intravitreal injections of 0.5mg ranibizumab at every scheduled visit from Day 0 to week 103. At week 104 all subjects will be seen, subjects who have reached the 12 week interval will be seen monthly and treated PRN. Subjects who have not achieved the 12-week interval, at week 104, will continue a treat and extend protocol until the 12 week interval is met. Once those subjects reach a 12 week interval, at any time during week 104 to week 156, they will then switch to monthly visits and treated PRN.

### **2.1 Primary Objective**

- Mean change in ETDRS visual acuity from baseline to weeks 24-28, baseline to weeks 48-56, baseline to weeks 72-82, baseline to week 104, baseline to weeks 128-132 and baseline to week 156.

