## 2.2 Secondary Objectives

- Incidence and severity of adverse events (ocular and non-ocular).
- Total number of intravitreal injections required from baseline through weeks 48-57 (week closest to week 52), baseline through week 104 and baseline through week 156.
- Total number of office visits and imaging studies performed from baseline through weeks 24-28 (week closest to week 26), baseline through weeks 48-56 (week closest to week 52), baseline through weeks 72-82 (week closest to week 78), baseline through week 104, baseline through weeks 128-132 (week closest to week 132) and baseline through week 156.
- Percentage of subjects with persistent active exudation on SD-OCT from baseline through weeks 48-57 (week closest to week 52), baseline through week 104 and baseline through week 156.
- Percentage of subjects with persistent leakage on fluorescein angiography from baseline through weeks 24-28, baseline to weeks 48-56, baseline to weeks 72-82, baseline to week 104, baseline to weeks 128- 132 and baseline to week 156.
- CNVM lesion size at baseline, compared to baseline to weeks 24-28, baseline to weeks 48-56, baseline to weeks 72-82, baseline to week 104, baseline to weeks 128-132 and baseline to week 156, as determined by fluorescein angiography.
- Mean change in central foveal thickness by SD-OCT from baseline to weeks 48-57, baseline to week 104 and baseline to week 156.
- Mean change in BCVA by ETDRS letter score from baseline through weeks 24-28, baseline through weeks 48-56, baseline through weeks 72-82, baseline to week 104, baseline through weeks 128-132 and baseline to week 156.

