#### **3.2 OVERVIEW OF STUDY DESIGN**

This trial will compare the results of 2 cohorts, with different treatment intervals, to assess the safety, tolerability and efficacy of IVT of ranibizumab for the treatment of wet AMD. Specifically, this trial will evaluate the ability to reduce the amount of visits and IVT ranibizumab treatments needed all while maintaining an exudation-free macula. Subjects in both cohorts will be followed for a total of 156 weeks.

**Cohort A** (control arm, monthly, n=20) Subjects will receive monthly treatment of IVT 0.5 mg ranibizumab from Day 0 to week 100. Monthly treatment is defined as every 28 days (±7 days). Dosing should not occur earlier than 21 days after the previous treatment.

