#### **Retreatment criteria for PRN phase**

Re-treatment will be initiated if any of the following criteria are meet:

- Presence of any abnormal intraretinal or subretinal fluid on high resolution SD-OCT.

- Presence of new intraretinal or subretinal hemorrhage related to AMD on examination.
- 10 letter loss from previous visit, related to active wet AMD in the opinion of the treating investigator

**Cohort B** (comparator arm, TREX, n=40) Subjects will receive a minimum of 3 consecutive IVT 0.5 mg ranibizumab (visits 2, 4 and 5). Starting at week 8, if a subject has achieved a “dry” macula; signs of active exudation have resolved by both ophthalmic exam and SD-OCT evaluation they will begin a Treat and Extend protocol.

For a macula to be considered “dry” it must meet both the following criteria:

1. Resolution of intraretinal and subretinal fluid
2. Resolution of all subretinal hemorrhage related to active exudative AMD

Resolution of pigment epithelial detachments (PED) is not required for a macula to be considered “dry”. Small intraretinal cystic areas observed on SD-OCT are acceptable and the corresponding macula can be considered dry. The criteria for these are specific; see reference images (Appendix D) for examples of acceptable intraretinal cystic spaces. When cysts described in Appendix D are present the macula should be considered dry and should be noted on the SD-OCT interpretation. Also, minimal increased retinal thickening on SD-OCT without definitive intraretinal or subretinal exudative fluid can be observed and the corresponding macula will be considered dry.

Once a “dry” macula is achieved the interval between visits is then lengthened by 2-week increments, at every visit the macula is “dry”. IVT ranibizumab will be rendered at every visit, no earlier than 7 days before the target date and no later than 7 days after the target date; the interval between visits is individualized based on each patient’s response to treatment. The interval between injections will not exceed 12 weeks

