## **4.2 METHOD OF TREATMENT ASSIGNMENT**

Subjects will receive open-label IVT of 0.5 mg ranibizumab. Subjects will be randomized into a 1:2 ratio that will occur at Day 0.

- Cohort A – Subjects will receive monthly treatment of 0.5 mg IVT ranibizumab for 100 weeks. Starting at week 104 subjects will receive PRN IVT ranibizumab for another 56 weeks (total of 156 weeks)
- Cohort B – Subjects will receive 0.5mg IVT ranibizumab for 3 a minimum of consecutive visits (visit 2, 4 & 5) followed by a treat and extend protocol in which follow-up intervals are increased when there is no clinical and SD-OCT evidence of disease activity by 2-week intervals. Starting at week 104, if a subject has achieve the 12 week interval they will switch to monthly visits with PRN IVT ranibizumab through week 156. If a subject has not achieved a dry macula they will continue the treat and extend protocol until the 12 week interval is met and then switch to monthly visits with PRN IVT ranibizumab.

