### Ocular Assessments (All Study Visits)

- Best Corrected Visual Acuity Visual function of the study eye and the fellow eye will be assessed using the ETDRS protocol (The Early Treatment Diabetic Retinopathy Study Group, 1985) at 4 meters. (See Appendix F)
- IOP measurement of both eyes will be measured pre-dilation at every visit. IOP will be measured post intravitreal injection 30 min ( $\pm$  15 min) in the study eye. The method used for a subject must remain consistent throughout study.
- Slit lamp examination-Subject's anterior eye structure and ocular adnexa will be examined at each study visit using a slit lamp by the investigator.
- Indirect Ophthalmoscopy the subject's posterior pole and peripheral retina will be examined by indirect ophthalmoscopy at each study visit pre dose by the investigator
- Subjects will receive 0.5 mg intravitreal injection of ranibizumab per treatment schedule
- Telephone Safety Check 3 days ( $\pm$  1 day) post injection (after first injection only)

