Auto Fluorescence	X	X	X	X	X	X	X	X	X	X	X	X	X	X
FP/ FA	X						X							X
CNVM	X						X							X
Measurement														
Study Drug Injection	X	X	X	X	X	X	X	X	X	X	X	X	X	X
Serum and/or Plasma Blood Draw														X

1. Injection administered on a PRN basis, if meets re-treatment criteria 2. Optional

Year 3 T-REX/PRN Treatment Schedule

Week (±7 days)	108	112	116	120	124	128	132	136	140	144	148	152	156
Visit	Visit	Visit	Visit	Visit	Visit	Visit	Visit	Visit	Visit	Visit	Visit	Visit	Visit
Vital Signs	30 X	31 X	32 X	33 X	34 X	35 X	36 X	37 X	38 X	39 X	40 X	41 X	42 X
Interval History (AE & Con Meds)	X	X	X	X	X	X	X	X	X	X	X	X	X
Indirect/Slit Lamp Exam	X	X	X	X	X	X	X	X	X	X	X	X	X
IOP (Pre & Post Injection)	X	X	X	X	X	X	X	X	X	X	X	X	X
Visual Acuity (ETDRS)	X	X	X	X	X	X	X	X	X	X	X	X	X
SD-OCT	X	X	X	X	X	X	X	X	X	X	X	X	X
Auto Fluorescence	X	X	X	X	X	X	X	X	X	X	X	X	X
Fundus Photo/ FA						X							X
CNVN Measurement						X							X
Study Drug Injection	X 												
Serum and/or plasma						X 							X 

1. Injection administered on a PRN basis, if meets re-treatment criteria      2. Optional

T-REX/Treat and Extend Arm/Cohort 2

		Week 12-156					
Week (±7 days)	Screen	Day0	Day7	4	8		
Visit	Visit	1	2	3	4	5	
Sign IFC	X						
Medical/Oph HX	X						
Vital Signs	X	X	X	X	X	X	
Interval History (AE & Con Meds)	X	X	X	X	X	X	
Indirect/Slit Lamp Exam	X	X	X	X	X	X	
IOP (Pre & Post Injection)	X	X	X	X	X	X	
Visual Acuity (ETDRS)	X	X	X	X	X	X	
SD-OCT	X	X	X	X	X	X	
Auto	X	X	X	X	X	X	
Fluorescence FP/FA	X						
CNVM Measurement	X						
Study Drug Injection 		X			X	X	
Plasma and/or Serum Sample 							

- Cohort 2 will receive 3 mandatory 0.5mg ranibizumab injections (Day 0, week 4, & week 8)
- Interval will remain at 4 weeks until there are no signs of exudative disease on SD-OCT or clinical examination
- Once a dry macula is achieved meaning there are no signs of exudative disease on SD-OCT or clinical examination the subject will start the Treat and Extend protocol, interval between injections is increased by 2-week intervals, starting at visit 6.
  - o Treatment Interval will not exceed > 12 weeks.
- If recurrent exudative disease is detected at any visit, after extension has been met, the interval between injections will decrease by 2 weeks (compared to the previous interval) until a "dry" macula is again established or subject is back at the 4-week interval.

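### No adjusted arm contrast is specified for acuity change, so response from the eight weeks of identical treatment would remain as avoidable noise; the loss is of precision, and its size is an assumption.

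*Combined protocol and SAP*

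**What the plan says.** The primary outcome is "Mean change in ETDRS visual acuity from baseline to weeks 24-28, baseline to weeks 48-56, baseline to weeks 72-82, baseline to week 104", then to weeks 128-132 and week 156. Sections 3.4.1 and 4.8.3 repeat it. A secondary outcome is "Mean change in central foveal thickness by SD-OCT from baseline to weeks 48-57, baseline to week 104 and baseline to week 156".

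On timing and treatment:

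- Section 4.2: "Subjects will be randomized into a 1:2 ratio that will occur at Day 0".
- Section 3.2, Cohort A: "Subjects will receive monthly treatment of IVT 0.5 mg ranibizumab from Day 0 to week 100".
- Section 3.2, Cohort B: "Subjects will receive a minimum of 3 consecutive IVT 0.5 mg ranibizumab (visits 2, 4 and 5". Appendix A, treat-and-extend schedule, gives the dates: "Cohort 2 will receive 3 mandatory 0.5mg ranibizumab injections (Day 0, week 4, & week 8".
- The same schedule says when the regimens can part: "interval between injections is increased by 2-week intervals, starting at visit 6", the visit after week 8.

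On data, Section 4.5.1 states under its all-visits heading that "Best Corrected Visual Acuity Visual function of the study eye and the fellow eye will be assessed using the ETDRS protocol", and it also requires SD-OCT at all visits. Appendix A marks both at Screening, Day 0, Day 7, week 4 and week 8 in each arm.

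On analysis, Section 4.8.1 lists descriptive summaries, states that tests are two-sided, and refers to a Statistical Analysis Plan for detail. No such detail appears in the supplied text. Section 4.8.4 specifies available cases without imputation. No covariate, model or adjusted contrast is named.

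**The concern.** Eyes differ in how much they improve over the first three injections. Because protocol treatment is the same in both arms over that period, those differences say nothing about monthly dosing versus treat-and-extend. If the arms are compared on raw change from baseline, the early response is part of every subject's outcome and adds to the variance of the contrast. Adjusting for the Day 0 score removes little of it, because Day 0 precedes the response. The week-8 score contains it.

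With 20 and 40 eyes, the width of the interval limits what the trial can say about whether extending the interval preserves vision. Precision available from scores already collected is worth prespecifying.

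**Working it through.** The plan has no power calculation, SD or margin to reproduce. The group sizes 20 and 40 are from Section 4.1.1. All SDs and correlations below are assumptions.

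**1. Multiplier.** SE of the arm difference = residual SD × sqrt(1/20 + 1/40) = residual SD × 0.274.

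**2. Model.** Day 0 = B + e; week 8 = B + R + e; endpoint = B + R + C + e, with independent errors at each visit. Assumed SDs in letters: B (true acuity) 12, e (measurement error) 4, R (early response) 8, C (later change) 10. The variances are 144, 16, 64 and 100. Let ρ be the correlation of R with C, so cov(R, C) = 80ρ.

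**3. Case ρ = 0.**

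- Raw change: 64 + 100 + 16 + 16 = 196; SE = 14.0 × 0.274 = 3.83.
- Adjusted for Day 0: endpoint variance is 144 + 64 + 100 + 16 = 324, and 324 - 144²/160 = 194.4; SE = 3.82.
- Adjusted for Day 0 and week 8: the two scores have variances 160 and 224 and covariance 144, so the determinant is 160 × 224 - 144² = 15,104. Their covariances with the endpoint are 144 and 208. Residual = 324 - (224 × 144² - 2 × 144 × 144 × 208 + 160 × 208²)/15,104 = 324 - 194.7 = 129.3; SE = 3.11.

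The reduction over Day 0 adjustment is 1 - 129.3/194.4 = 33%. With 1.96 the 95% half-width goes from 7.5 to 6.1 letters; t quantiles make both slightly wider.

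**4. Dropping independence.** The endpoint variance becomes 324 + 160ρ, and its covariance with week 8 becomes k = 208 + 80ρ. The Day 0 residual is 324 + 160ρ - 129.6. The two-score residual is step 3's expression with 324 + 160ρ in place of 324 and k in place of 208. Equivalent N is 60 × the ratio of the two residuals.

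| ρ | Endpoint variance | k | Residual, Day 0 | Residual, Day 0 + week 8 | Reduction | Equivalent N |
|---|---|---|---|---|---|---|
| 0 | 324 | 208 | 194.4 | 129.3 | 33% | 90 |
| -0.3 | 276 | 184 | 146.4 | 115.1 | 21% | 76 |
| -0.5 | 244 | 168 | 114.4 | 98.8 | 14% | 69 |
| -0.8 | 196 | 144 | 66.4 | 64.2 | 3% | 62 |

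A negative ρ is plausible: an eye that gains most early may have less left to gain. A positive ρ would raise the gain above 33%.

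**5. Varying the SDs.** With ρ = 0, early-response SD from 5 to 11 and later-change SD from 8 to 13, the reduction runs from 12% to 56%. Because ρ is fixed at zero, 12% is not a lower bound.

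**6. A second parameterisation.** Take equal SDs of 14 letters, with correlations 0.7 (Day 0 with week 8), 0.5 (Day 0 with endpoint) and 0.7 (week 8 with endpoint). A simulation of 5,000 trials gave an SD of the arm contrast of 3.84 for raw change, 3.33 adjusting for Day 0 and 2.79 adjusting for both. Here Day 0 adjustment alone helps appreciably. Over eight sets of correlations, the two-score adjustment left 43% to 89% of the variance left by Day 0 adjustment.

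**7. Break-even.** Adjusting change for the week-8 change costs one degree of freedom. It pays once the correlation between week-8 change and endpoint change exceeds about 0.13.

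**The case against.** - **A definition is not an error term.** Section 2.1 defines an outcome, and no section states an unadjusted test. A reader might infer that change from baseline is itself the fault, or that the plan commits to ignoring the week-8 scores. The documents support neither reading. The loss arises only if the contrast is unadjusted, and Section 4.8.1 refers to a plan whose detail is not in the supplied text. What stands is that the supplied text names no adjustment.
- **The size is not known.** A reader might take from the ρ = 0 row that the trial forgoes the equivalent of 30 subjects. That depends on assumed SDs and on early and later change being unrelated, and the gain nearly vanishes at strongly negative correlations. One figure also cannot serve six time points running to week 156, and nothing here quantifies foveal thickness. This objection stands in full.
- **Week 8 is after randomisation, in an open-label trial.** No masking of acuity examiners is described. If knowing the arm affects early scores or early dropout, adjusting for week 8 or forcing a common mean through week 8 could introduce bias. A Day-0-only analysis beside it does not fully settle this, since with 20 and 40 eyes a discrepancy could be noise. The risk is small, because protocol treatment is identical to that point, but it is a reason to show both estimates.
- **The trial stays imprecise.** With an assumed SD of 12 letters, power for a 5-letter difference is 33% unadjusted and only 57% when week-8 change and endpoint change correlate at 0.7. This is true, and it limits the benefit.

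**Conclusion.** The point holds as a matter of precision. Randomisation at Day 0, identical injections through week 8, acuity and SD-OCT at every visit, and no named adjustment are all in the documents. It follows that an unadjusted contrast of change would keep shared early response as noise.

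Under the stated SDs, the variance reduction over Day 0 adjustment is about 33% with independence, falling to 21%, 14% and 3% at correlations of -0.3, -0.5 and -0.8. It is probably smaller at weeks 104 to 156, when more time separates the endpoint from week 8 and Cohort A has moved to PRN treatment. A reader might infer that the primary result would be biased or invalid; nothing in the documents supports that. This is an inexpensive improvement.

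**What to change.** In Sections 2.1, 3.4.1 and 4.8.3, keep mean change from baseline as the outcome and descriptive summary, and name Day 0 as the baseline score. Then prespecify:

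- The between-arm difference at each time point, estimated from a model adjusted for the Day 0 score.
- A second analysis that also uses the week-8 score taken before that visit's injection. It enters either as a covariate or through a longitudinal model with a common mean for both arms through week 8, which also keeps subjects who miss week 8.
- The same pair of analyses for central foveal thickness.
- Both estimates reported side by side, with a comparison of the arms on week-8 score and on missingness at week 8.

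The cost is analysis wording, settled before the data are analysed; no visits or measurements are added. The small downside is reliance on a post-randomisation score in an open-label trial, which the paired reporting makes visible but cannot rule out.
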